8.0 STATISTICAL ANALYSIS PLAN

The primary goal of the study is to characterize the safety and establish the recommended phase 2 dose (RP2D) and preliminary efficacy evaluation with a total of 24 evaluable subjects. A modified 3+3 design with a cohort size of 6 with a continuous toxicity monitoring. The design is to inform de-escalation decisions based on safety if needed. For the purposes of this trial, a target toxicity rate of approximately 33% will be used to establish the RP2D. Table 7 below provides the probability of detecting the number of DLTs based on true toxicity rates with 24 subjects:

Table 7 Number of DLTs and the Corresponding Cumulative Probability for SeveralToxicity Rates with 24 Subjects

True toxicity rate (%)	Corresponding Number of	Cumulative Probability for
	DLTs (# DLT)	Detecting #DLT
20	5	0.66
25	6	0.56
30	7	0.56
35	8	0.53
40	10	0.65

Safety Analyses

All patients who received any protocol therapy will be employed for safety analyses. Patient incidence of all treatment-emergent AEs will be tabulated by dose and system organ class and preferred term. Tables of fatal adverse events, serious adverse events, treatmentrelated AEs, and adverse events leading to withdrawal from investigation product will also be provided. The MedDRA will be used to code adverse events and the NCI CTCAE version 4.0 will be used to grade severity of adverse events and laboratory toxicities.

Summary statistic will be provided for total number of subjects treated under each dose, average dose administered, and duration of treatment.

For select laboratory parameters, changes of laboratory values over time (eg, change from baseline summary statistics), grade shifts in laboratory values from baseline to worst onstudy value, and grade 3 or higher laboratory toxicities will be summarized. The ECG measurements from this study will be performed as per standard of care for routine safety monitoring.

Efficacy analysis

The efficacy analysis population consists of all subjects who receive at least one cycle treatment (3-day doses of study treatment).

Tcell subsets (CD4, CD8, Treg) and MDSC subsets (CD14+, CD15+) will be analyzed by flow cytometry at each of the blood draws time points and compared to whole blood cells, total lymphocytes and monocytes populations between time points and compared between pretreatment, on treatment and post treatment. T cell activation will be assessed by CD107 and IFNg production in response to PMA and ionomycin and compared between pretreatment, on treatment. MDSC functional assays will assess the ability of MDSC's to suppress stimulated T cell proliferation as a percent of positive control and will be compared between time points and compared between the points and compared

Linear mixed effects models will be used to assess the frequency of MDSC subsets over times. Contrast statements will be used to estimate changes in the frequency of MDSC subsets and its suppressive function from baseline after treatment at different time points. For PFS endpoint, Kaplan-Meier (KM) curves and median estimates from the KM curves will be provided as appropriate. Subjects without efficacy evaluation data or without survival data will be censored at Day 1. The change in frequency of T cell subsets, the expression of activation markers, and the CTL response will be evaluated using paired t-test. Correlations between the frequencies of MDSCs and T cell subsets or expression of activation markers will be evaluated using Pearson or Spearman Correlation Coefficients at a specified time points. Alternatively, Intraclass correlation coefficients will be used to assess the potential correlations among those measurements over time.

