6.6.2 Subject Discontinuation

A subject must be discontinued from the trial for any of the following reasons:

- The subject or legal representative (such as a parent or legal guardian) withdraws consent
- Confirmed radiographic disease progression (i.e. progressive disease per RECIST 1.1 as documented by tumor imaging at any time point). Subjects with disease progression indicated on imaging should discontinue all study treatment, but may continue pembrolizumab according to standard of care outside of the study at investigator discretion. Subjects with suspected clinical progression may continue study treatment at investigator discretion until there is radiographic confirmation of disease progression.
- Unacceptable adverse experiences as described in Section 6.1.1.2 (*Dose Modification (Escalation/Titration/Other)*)
- Intercurrent illness that prevents further administration of treatment
- Investigator's decision to withdraw the subject
- The subject has a confirmed positive serum pregnancy test
- Noncompliance with trial treatment or procedure requirements
- The subject is lost to follow-up

• Administrative reasons

The End of Treatment (EOT) and Follow-up visit procedures are listed in Section 7.1 (*Trial Schedule of Events Chart*) and Section 7.2.7 (*Visit Requirements*). Additionally, all subjects will be followed for overall survival until death, withdrawal of consent, or the end of the study, whichever occurs first.

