7.1 Trial Schedule of Events Chart

Trial Period:	Screening Phase	Treatment Cycles			8	Post-Treatment				
Treatment Cycle/Title:	Screening	1	2	3	4	5+	EOT ⁱ	Safety Follow-up 1	Safety Follow-up 2 ^b	Survival Follow-up
Scheduling Window (Days):	-28 to -1		± 7	±7	± 7	± 7	± 7	30 days (+ 2 days) post last treatment or prior to starting new treatment	90 days (+ 7 days) post last treatment	Every 12 weeks (+ 14 days)
CBC with Differential ^g	Х	х	Х	х	Х	х				
Comprehensive Serum Chemistry Panel ^{e & g}	х	x	x	x	x	х				
T3, FT4 and TSH ^g	Х	х		х		xf				
Efficacy Measurements										
Tumor Imaging ^c	х					х	х			
Tumor Biopsies/Archival Tissue Collection/Correlative Studies Blood										
Optional Archival or Newly Obtained Tissue Collection ^d	х							х	x	х
Correlative Studies Blood Collection	х		x		x	x ^j		x ^j		

^a Administered according to schedule outlined in table 2. Vesanoid drug supply will be dispensed in clinic on Cycle 1 Day -1 for Cycle 1, Cycle 1 Day 0 for Cycle 2, Cycle 2 Day 0 for Cycle 3 and Cycle 3 Day 0 for Cycle 4.

^b To be completed only for subjects who have not initiated a new therapy. Can be collected at a regularly scheduled clinic visit or via patient contact by telephone.

^e Tumor imaging generally performed every 12 weeks per standard of care for the clinic and evaluated by RECIST 1.1 criteria (Section 11.3 - *Appendices*). Baseline tumor imaging should be completed within 28 days of starting treatment; however, exceptions may be approved after discussion with the principal investigator. Brain metastases that were radiated prior to starting the trial should be re-imaged at the standard 12 week frequency, or as deemed clinically appropriate, by the treating physician.

^d Optional additional tissue collection will be obtained from archival or future biopsies if available.

^e To include lactate dehydrogenase at screening.

^f To be collected every other cycle per standard of care for clinic.

^g Screening labs should be performed within 10 days of treatment initiation.

^h Within 72 hours prior to receiving the first dose of study medication.

ⁱTo be completed when it is decided that the subject will discontinue study treatment. Tumor imaging is only required at investigator's discretion. This visit can be combined with the first safety follow-up visit if the subject is planning to start a new treatment.

 $j \le 60$ days after last Vesanoid treatment.

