7.2.3 Efficacy Measurement

7.2.3.1 Tumor Imaging and Assessment of Disease

Following the standard of care for pembrolizumab treatment, imaging will be performed at the treating physician's discretion. The imaging will be reviewed by the investigator according to the RECIST criteria (version 1.1), to monitor the appearance of new metastatic lesions and the size of existing lesions.

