7.2.7.3 Post-Treatment Visits

7.2.7.3.1 Safety Follow-Up Visits

Subjects who discontinue trial treatment will move into the follow-up phase and other treatment decisions will be at the discretion of the treating physician.

The first safety follow-up visit will be conducted for all subjects 30 days after the last dose of trial treatment (VESANOID and/or pembrolizumab) or before the initiation of a new anti-cancer treatment, whichever comes first.

Should the subject not initiate a new anti-cancer treatment, the second safety follow-up visit will be conducted 90 days after the last dose of trial treatment. All AEs that occur prior to the Safety Follow-Up Visits should be recorded. Subjects with an AE of Grade > 1 will be followed until the resolution of the AE to Grade 0-1 or until the beginning of a new anti-neoplastic therapy, whichever occurs first. SAEs that occur within 90 days of the end of treatment or before initiation of a new anti-cancer treatment should also be followed and recorded.

7.2.7.3.2 Survival Follow-up

Subjects should be contacted at regularly scheduled clinic visits or by telephone every 12 weeks to assess for survival status until death, withdrawal of consent, or the end of the study, whichever occurs first. Every effort should be made to collect information regarding disease status and post-study anti-neoplastic treatment.

Patients will be followed for up to 2 years or until recurrence or death.

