11.1 ECOG Performance Status

11.2 Common Terminology Criteria for Adverse Events V4.0 (CTCAE)

The descriptions and grading scales found in the revised NCI Common Terminology Criteria for Adverse Events (CTCAE) version 4.0 will be utilized for adverse event reporting. (http://ctep.cancer.gov/reporting/ctc.html)

11.3 Response Evaluation Criteria in Solid Tumors (RECIST) 1.1 Criteria for Evaluating Response in Solid Tumors

RECIST version 1.1* will be used in this study for assessment of tumor response. While either CT or MRI may be utilized, as per RECIST 1.1, CT is the preferred imaging technique in this study.

* As published in the European Journal of Cancer:

E.A. Eisenhauer, P. Therasse, J. Bogaerts, L.H. Schwartz, D. Sargent, R. Ford, J. Dancey, S. Arbuck, S. Gwyther, M. Mooney, L. Rubinstein, L. Shankar, L. Dodd, R. Kaplan, D. Lacombe, J. Verweij. New response evaluation criteria in solid tumors: Revised RECIST guideline (version 1.1). Eur J Cancer. 2009 Jan;45(2):228-47.

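### The only PFS censoring rule has no exception for a recorded death, so on its most natural reading a treated patient who dies before the first post-baseline scan drops out of the Kaplan-Meier curve

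*Combined protocol and SAP*

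**What the plan says.** Section 8.0 (Efficacy analysis) plans a Kaplan-Meier curve and median for PFS and then gives the only censoring rule in the documents: "Subjects without efficacy evaluation data or without survival data will be censored at Day 1". The efficacy population in the same section is everyone who received one cycle, meaning the 3-day course; no scan is required. Section 4.2.3 names PFS as one of two efficacy endpoints, and Section 3.2 places it under a secondary objective.

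On imaging, a footnote to the Section 7.1 chart says "Tumor imaging generally performed every 12 weeks per standard of care for the clinic", while Section 7.2.3.1 says "imaging will be performed at the treating physician's discretion". The chart marks tumour imaging at screening, at cycle 5 onward and at end of treatment, where a footnote leaves it to the investigator's discretion. No imaging is marked in cycles 1 to 4.

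On deaths, Section 6.6.2 says "all subjects will be followed for overall survival until death, withdrawal of consent, or the end of the study", and Section 7.2.7.3.2 provides for contact at clinic visits or "by telephone every 12 weeks to assess for survival status until death".

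Progression is tied to RECIST 1.1: Section 6.6.2 has "progressive disease per RECIST 1.1 as documented by tumor imaging at any time point", and Section 11.3 adopts the same criteria. Nowhere do the documents say that death is a PFS event, or from which date PFS is counted.

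**The concern.** The rule joins two conditions with *or* and repeats *without*, so grammatically either gap alone triggers censoring at Day 1. A patient who completes the first 3-day course and dies at, say, week 6 would usually have a known death date and no post-baseline scan. If efficacy evaluation data means such a scan, that patient meets the first condition and leaves the risk set before contributing anything. An early death is among the worst PFS outcomes, and the rule would treat it as no information.

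What is at stake is the reported PFS curve and its median. No hypothesis test, error rate or dose decision uses PFS.

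**Working it through.** The plan states no PFS event count, power or target median, so there is no figure of its own to reproduce. The check has two parts: what the sentence covers, and how far it could move the curve.

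**What counts as efficacy evaluation data**

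- *A post-baseline tumour assessment.* The sentence directly follows the PFS sentence. In the Section 7.1 chart the efficacy measurements block contains only tumour imaging, and Section 7.2.3, headed as efficacy measurement, also deals only with imaging. This is the most natural reading, and it censors the unscanned death.
- *Any tumour scan, including baseline.* Imaging is marked at screening. A patient with a baseline scan and a recorded death then has both kinds of data and escapes the rule.
- *MDSC blood draws as well.* Section 4.2.3 counts MDSC subsets as efficacy, and blood is drawn at cycles 2 and 4. A patient who reached cycle 2 before dying would escape.
- *Only subjects with neither kind of data.* Every recorded death escapes. The wording has *or*, so it does not say this.

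**When the first scan falls.** Four cycles of 3 weeks put the start of cycle 5 at 4 × 3 = 12 weeks. The first post-baseline scan is therefore generally at about week 12, earlier or later at the physician's discretion.

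**Effect on the natural reading**

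Inputs: n = 24 (Section 2.1, taken as the size of the efficacy population); k = number of treated patients who die before a post-baseline scan. The documents do not give k, so it is an assumption. Eligibility at ECOG 0 or 1 (Section 5.1.2) suggests it is small; 0 to 2 is shown. No other censoring occurs before these deaths, and no event occurs by Day 1.

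After the k deaths and m other events:

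- deaths counted as events: S = (24 − k − m)/24
- rule on the natural reading: S = (24 − k − m)/(24 − k)
- ratio: 24/(24 − k), whatever m is

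| k | Ratio | A true 50.0% reads | True curve value at the reported median, 0.5 × (24 − k)/24 |
|---|---|---|---|
| 0 | 1.000 | 50.0% | 50.0% |
| 1 | 24/23 = 1.043 | 52.2% | 47.9% |
| 2 | 24/22 = 1.091 | 54.5% | 45.8% |

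**Median.** Take a median that falls after these deaths, with events one at a time and no censoring before it. Counted correctly it is the 12th event. Under the rule, k = 1 needs 12 of the other 23, plus the death: the 13th event. For k = 2 it needs 11 of the other 22, plus the two deaths: again the 13th.

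With progressions grouped at scans at weeks 12, 24 and 36 (assumed counts, everyone else event-free):

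| k | Progressions at weeks 12, 24, 36 | Median, deaths as events | Median, rule on the natural reading |
|---|---|---|---|
| 1 | 8, 3, 2 | 24 weeks (12/24 = 0.500) | 36 weeks (12/23 = 0.522 at 24; 10/23 = 0.435 at 36) |
| 1 | 6, 3, 3 | 36 weeks (11/24 = 0.458) | 36 weeks (11/23 = 0.478) |
| 2 | 10, 2, 2 | 12 weeks (12/24 = 0.500) | 24 weeks (12/22 = 0.545 at 12; 10/22 = 0.455 at 24) |
| 2 | 8, 3, 2 | 24 weeks (11/24 = 0.458) | 24 weeks (11/22 = 0.500) |

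The median stays put or moves to the next scan.

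**Before the death.** Take one progression at week 6 and one unscanned death at week 10. In weeks 6 to 10 the correct value is 23/24 = 0.9583 and the value under the rule is 22/23 = 0.9565, slightly lower. From week 10 the correct value is 22/24 = 0.9167 and the rule still gives 0.9565, the expected ratio of 1.043.

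**Sampling error for scale.** The 95% half-width near 50% is 1.96 × √(0.25/24) = 0.200, or 20 points, against shifts of 2.2 and 4.5 points.

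**The case against.** The strongest reply is that the sentence never says *post-baseline*. The chart marks tumour imaging at screening, and MDSC draws at cycles 2 and 4 are arguably efficacy data too. Intent also points the other way: taken literally, *or* would censor at Day 1 even a patient with documented RECIST progression whose survival data are missing, which can hardly be meant. Asking for survival data in a PFS rule suggests that deaths were expected to feed into PFS. On this view the sentence is an ordinary fallback for subjects who contribute nothing.

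This stands in part. A reader might infer that the plan certainly discards every death before a first scan. The documents do not support that, because the key term is undefined and two or three readings avoid the problem wholly or partly. But the ambiguity remains: two programmers could follow the sentence and draw different curves, and no other rule or event definition decides between them. Assuming that PFS conventionally includes death does not help, since this sentence would still censor the unscanned death on the natural reading.

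A reader might also infer that the distortion is favourable everywhere on the curve. It is not: before the death the curve can be very slightly too low if another patient progresses first. The one-directional statement holds only for curve values after the deaths, and for a median that falls there.

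**Conclusion.** The point holds as a minor wording defect. The only PFS censoring rule makes no exception for a recorded death and rests on an undefined term. On the most natural reading, k unscanned deaths among 24 raise every later curve value by the factor 24/(24 − k), and a later median either stays the same or lengthens.

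This assumes that efficacy evaluation data means a post-baseline tumour assessment, that the patients concerned completed the 3-day course (otherwise they are outside the efficacy population), that their deaths were recorded, and that there is no other early censoring. The documents do not give k, and with k = 0 nothing changes. For k = 1 or 2 the shift is well inside the sampling error. It would be wrong to conclude that the trial's efficacy finding is materially inflated or that its safety and dose conclusions are affected: PFS here is secondary and descriptive.

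**What to change.** Replace the censoring sentence in Section 8.0 with:

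> PFS is the time from first dose of study treatment to the earlier of RECIST 1.1 progression or death from any cause. A death before any post-baseline tumour assessment is an event at the date of death. Only subjects with neither a post-baseline tumour assessment nor a recorded death are censored at first dose.

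Report the number of subjects censored at first dose. Stating that other event-free subjects are censored at their last evaluable tumour assessment would be a useful clarification, but it is not part of this defect.

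The cost is SAP text only, since survival status is already collected; no visits, scans or patients are added. The downside is that the PFS estimate may be slightly less favourable. If the sponsor always meant to count these deaths, the edit only makes that explicit.

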2.0 TRIAL DESIGN

2.1 Trial Design

This is a Phase I/Ib investigator-initiated open label trial of the combination of VESANOID and pembrolizumab treatment.

A total of 24 evaluable patients will be recruited into the study. All the patients will receive 200mg Q3W pembrolizumab treatment plus the supplemental treatment of 150 mg/m² VESANOID orally for 3 days surrounding each of the first four infusions of pembrolizumab (day -1, day 0, day +1) for a total of 12 days of VESANOID treatment (Section 2.2 *Trial Schema/Diagram*).

To closely monitor DLTs, subjects will be recruited into the study using a cohort size of 6. The toxicity monitoring design is to inform de-escalation decisions based on safety if needed. DLTs will be assessed during the DLT assessment window of 21 days following the first dose of Vesanoid and Pembrolizumab (Cycle 1 Day 0 to Cycle 2 Day 0). Patients who withdraw from the study prior to completing the DLT assessment window for any reason other than a DLT will be replaced. See Section 6.1.1.2.3 for DLT definition.

After the first 6 subjects in cohort 1 complete the DLT period, the Sponsor-Investigator will review data pertaining to the dose de-escalation decision. Available adverse event data and laboratory assessments will be used to determine whether the Vesanoid dose should be continued at 150 mg/m^2 or whether the Vesanoid dose should be de-escalated to 100 mg/m^2 in the subsequent six subjects to be enrolled in cohort 2.

Dose de-escalation will proceed in accordance with the following rules:

- 6 patients will be treated in cohort 1.
 - If 0-2 patients experience a DLT in cohort 1, the Vesanoid dose will be maintained.
 - \circ If \geq 3 patients in cohort 1 experience a DLT, then dose de-escalation of Vesanoid will proceed.
- 6 additional patients will be treated in cohort 2 at either the starting Vesanoid dose (150 mg/m²) or the reduced Vesanoid dose (100 mg/m²).
 - If 0-2 patients experience a DLT in cohort 2, the Vesanoid dose will be maintained.
 - If \geq 3 patients in cohort 2 experience a DLT, then the study will stop.
- If it is determined that the dose will be maintained from Cohort 2, then an additional cohort (cohort 3) of up to 12 patients (depending on the number of patients required to achieve the enrollment goal of 24 patients, but not to exceed 30 patients) will be treated at either the starting Vesanoid dose (150 mg/m²), or the reduced Vesanoid dose (100 mg/m²).

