This trial will be conducted in compliance with this protocol, Good Clinical Practice, and local and federal regulations.

Anticipated total number of enrolled research subjects: up to 30 to allow for screen fails or withdrawals

Anticipated number to complete study: 24 (who receive at least one dose of VESANOID and Pembrolizumab)

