2.2 Trial Schema/Diagram

Proposed schedule for treatment and blood draws.

Figure 1. Diagram of the treatment and blood draw schedule for this study. Patients will receive pembrolizumab infusions every three weeks. Patients will also receive 3 days of VESANOID treatment surrounding each of the first 4 infusions of pembrolizumab, beginning one day prior to the infusion (a total of 12 days of VESANOID). Six tubes of peripheral blood (for a total of approximately 40 ml) will be drawn at enrollment, at the 2rd and 4th infusions, and within 60 days of the final VESANOID dose for additional functional experiments.

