7.2.5 Laboratory Procedures/Assessments

7.2.5.1 Standard safety laboratory tests.

Will be obtained as outlined in section 7.1 - Trial Schedule of Events.

7.2.5.2 Experimental lab draws.

Will be performed at regularly scheduled clinic visits as outlined in section 2.2 - *Trial Schema/Diagram*. Peripheral blood mononuclear cells (PBMCs) will be isolated and flow cytometry will be used to quantify MDSCs and T cells.

- **Baseline immune response determination.** Subjects in the study will be asked to provide 40 mls of blood prior to initiating treatment to evaluate baseline immune responses and immune cell frequencies.
- **Immune response monitoring.** Blood samples will be drawn prior to the administration of the 2nd and 4th doses of pembrolizumab and after the last dose of VESANOID for continued measurement of immune cell frequencies.
- **Cytokine analysis.** Up to 20 ml of plasma will be stored for up to five years following study completion for subsequent cytokine analysis.

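### T-cell change is tested with complete-pair t-tests although MDSC from the same draws gets a mixed model: a cheap inconsistency to remove, with possible bias of unknown size and sign

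*Combined protocol and SAP*

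**What the plan says.** Under the efficacy analysis in Section 8.0, the T-cell markers are handled thus: "The change in frequency of T cell subsets, the expression of activation markers, and the CTL response will be evaluated using paired t-test". The visits to be paired are not named. In the same paragraph, "Linear mixed effects models will be used to assess the frequency of MDSC subsets over times", with contrast statements for change from baseline in MDSC frequency and suppressive function. The covariance structure and the coding of time are not given.

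Both families of markers come from the same samples. Section 8.0 says T-cell and MDSC subsets "will be analyzed by flow cytometry at each of the blood draws time points". Section 2.2 sets four draws: blood "will be drawn at enrollment, at the 2rd and 4th infusions, and within 60 days of the final VESANOID dose". Section 7.2.5.2 agrees on the two on-treatment draws: "Blood samples will be drawn prior to the administration of the 2nd and 4th doses of pembrolizumab".

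Section 8.0 defines the efficacy population as all who receive at least one three-day treatment cycle, with no requirement for complete pairs. Its one missing-data rule censors PFS at Day 1. Nothing covers a missed immune sample.

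**The concern.** A paired t-test keeps a patient only if both of its visits are present. Someone sampled at enrollment and infusion 2 but not later contributes nothing to a baseline-to-infusion-4 or baseline-to-last-draw comparison, although the infusion 2 value says something about the later one. A likelihood-based mixed model uses that value.

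Three things follow. The T-cell estimate can describe a smaller set of patients than the defined efficacy population. It loses precision. It is biased if the patients without the later draw differ in T-cell change from those with it. There is also a mismatch between linked results: Section 8.0 plans correlations between MDSC and T-cell markers, yet the estimates of change in the two would rest on different patients.

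The stakes are modest. Section 3.3 makes the T-cell objective exploratory, and no dose decision or error rate rests on it.

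**Working it through.** There is no figure to reproduce: the plan gives no effect size, SD, power or missing-sample rate for the T-cell analysis.

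**Timing, from the documents.** With three-week cycles the draws fall at enrollment, about day 21 (infusion 2), about day 63 (infusion 4), and up to day 64 + 60 = 124. Routine imaging every 12 weeks (Section 7.1) first falls at 12 × 7 = day 84.

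**Loss allowance.** Section 2.1 plans 24 evaluable patients and enrollment of "up to 30 to allow for screen fails or withdrawals", so at most (30 - 24)/30 = 20%, screen failures included. This is not a rate of missed draws. I therefore assume 10-30%.

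**Precision.** At 10%, 20% and 30% missing, 24 patients leave about 22, 19 and 17 pairs. Relative to complete data, the standard error grows by √(24/22) = 1.04, √(24/19) = 1.12 and √(24/17) = 1.19, for the same SD of change. A mixed model recovers part of this, not all.

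**Direction of bias.** Assume four visits with SD 1, equal correlation ρ, a true change of +0.5 SD, the last draw missing in 20%, and logistic missingness with slope 1.5 per SD. Bias in the last-visit change, from 200,000 simulated patients per scenario, shown as ρ = 0.5 / ρ = 0.7:

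| Who misses the last draw | Complete pairs | Maximum likelihood, all visits |
|---|---|---|
| Unrelated to outcome | 0.00 / 0.00 | 0.00 / 0.00 |
| Small observed earlier rise | +0.11 / +0.08 | 0.00 / 0.00 |
| Large observed earlier rise | -0.12 / -0.08 | 0.00 / 0.00 |
| Low baseline | -0.11 / -0.06 | 0.00 / 0.00 |
| Small unseen final rise | +0.23 / +0.15 | +0.15 / +0.10 |

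A hand check agrees. Write D for change from baseline. Then Var(D) = 2(1-ρ) and two changes from the same baseline have covariance 1-ρ, so the slope of the last change on the earlier one is 1/2. At ρ = 0.5, selection on D leaves a retained mean shift of 0.23. Selection on the last change itself therefore gives +0.23, and selection on the earlier change gives 0.23/2 = +0.11. For selection on baseline the slope is ρ-1: -0.5 × 0.23 = -0.11 at ρ = 0.5, and -0.3 × 0.23 = -0.07 at ρ = 0.7 (simulated -0.06).

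Over 10-30% missing, the complete-pair bias runs from about -0.16 to +0.32 SD.

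**Choice of covariance.** In a second simulation patients differ in their response: true change 0.5, response SD 0.6, intercept SD 0.7, residual SD 0.3-0.7. Between 10% and 30% leave after infusion 2, depending on the observed infusion 2 change (slope 1.5-3). Bias in the later change was:

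- paired: about +0.06 to +0.33
- random-intercept mixed model: about +0.02 to +0.11
- unstructured covariance: about 0

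At 24 patients the random-intercept model had lower root mean squared error than the paired estimate in every setting. The positive sign here is a consequence of the assumed mechanism.

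**The case against.** A reader might infer that patients lost to progression drop out and that the T-cell rise is therefore overstated. The documents do not establish either step.

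- The day 21 and day 63 draws come before routine imaging at about day 84.
- Section 6.6.2 lets patients with suspected clinical progression continue until imaging confirms it.
- Section 6.1.1.2 lets patients who stop VESANOID for toxicity continue pembrolizumab, so visits go on.
- The schedule allows the last draw at cycle 5 or later or at the first safety follow-up, which Section 7.2.7.3.1 plans for everyone.
- The sign depends on who is lost. The subsets include Treg, and no direction is stated for any marker, so a rise is not even the expected result for all of them.

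All of this stands. It does not rule out informative loss. Section 7.2.3.1 leaves imaging to the physician's discretion, a patient who stops before cycle 4 has no scheduled infusion 4 draw, and survival follow-up includes no correlative blood draw.

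Two further objections have weight. Giving the fuller model to MDSC, a secondary objective and named efficacy endpoint, is a defensible ranking. And the mixed model is not a cure: a random intercept alone leaves part of the bias, and loss that depends on the unseen value is only partly corrected. The first lowers the severity, but the ranking is no reason to withhold a model already being fitted to the same draws. The second determines how the fix must be worded.

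**Conclusion.** The complete-pair restriction, its mismatch with the efficacy population and the inconsistency with MDSC all follow from the text. That the T-cell estimate is biased does not. It may be, if draws are missed and loss is related to T-cell change, in a direction that depends on the pattern.

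The figures are illustrative and rest on assumed correlations, variances, loss rates and mechanisms. If loss is unrelated to outcome, the bias is zero and only precision suffers. Where loss depends on observed values, a suitably specified likelihood model removes the bias. Where it depends on the unseen last value, the model removes about a third (+0.23 to +0.15 at ρ = 0.5 and 20% missing). This is a cheap improvement to an exploratory analysis, of low severity.

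**What to change.** In Section 8.0, replace the paired t-test with the mixed model and baseline contrasts already planned for MDSC, applied to T-cell subsets, activation markers and CTL response and using every available visit. State visit as a categorical effect and an unstructured, or otherwise suitably flexible, covariance. Name the contrasts (infusion 2, infusion 4 and last draw, each against baseline). Transform skewed markers. Report the number sampled at each visit, and add a simple sensitivity analysis for loss related to unseen values.

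The cost is SAP wording, with no new samples or visits. An unstructured covariance over four visits has 4 × 5/2 = 10 parameters, against 2 for a random intercept. That is some burden with 24 patients, so name a simpler flexible structure as a fallback if the model does not converge. If no draw is missed, the unstructured model returns the same mean change as the paired comparison, so nothing is lost.
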